The SYNSEQ study intends to assess the positive LV dP/dt max achieved by multiple LV pacing either simultaneously or sequentially in comparison to the response achieved by the current (standard) BiV pacing configuration. The protocol includes rigorous methodology to decrease measurement variability and to be patient-tailored (e.g. AV-delay) in order to provide a justified conclusion to the acute hemodynamic benefit of MultiSpot Pacing (MSP) ²⁰. In addition, only "difficult" CRT patients are selected in order to adequately address the potential benefit of MSP in this patient population. The term "difficult" represent those patients with an increased likelihood of non-response to conventional CRT (e.g. ischemic patients or non-LBBB LV dyssynchrony patients). In addition to the hemodynamic evaluation, electrical parameters such as Q-LV/RV timing and QRS-width will be measured.

The study will also evaluate the feasibility of non-invasive sensors to assist with optimal lead placement and pacing sequence. Additionally, it is anticipated that this study will provide data that can be used to design future studies.

For further literature review, pre-clinical testing and previous clinical experience please refer to the Investigator’s Brochure.

B.2 Device information

B.2.1 Pacing devices

In order to deliver pacing on 4 different regions on the heart a system was developed which consists of a “master” pacer and four “slaves” pacers (Figure 1 and Table 1).

The master pacer is the 2290 analyzer (in the 2090 Programmer) which will be used to pace the right atrium (RA). The other pacing output (i.e. the ventricular) of the 2290 analyzer will be used as an atrial input for the up to four “slaves”. The “slaves” are used to pace the right ventricle (RV) and the three LV electrodes. The master pacer can be used to adjust AV-delay for all “slaves”. The “slaves” are hand-held pacers (Medtronic model number: 5388 DDD or 5392) and can be programmed independently. In this study the “slaves” will be programmed to specific settings before start of the experimental protocol. During the entire protocol the “slaves” will be either turned “on” or “off”. No additional intra-protocol settings will be changed. Benchmark testing performed has found that upon pacing, i.e using all four “slaves” the delay between them was ~1 ms (range 0-2 ms).

[figure not shown]

Figure 1: SYNSEQ equipment set-up. Green depicts the connection box.

B.2.2 Leads and electrophysiological catheters

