In summary, potential sources of bias that may be encountered in this clinical investigation have been considered and minimized by careful study design.

C.6 Randomization and blinding

No randomization and no blinding are used in this study.

C.7 Sample size

The sample size calculation is based on the primary objective 1. This study is powered to show superiority of MultiSpot SYN pacing to BiV pacing (standard CRT) for the primary endpoint % change + LV dP/dt max from baseline (AAI pacing). Assuming an expected difference in % change between MultiSpot and BiV pacing of 3.5% and standard deviation

of 7%, 34 patients would have 80% power to demonstrate superiority. The total sample size is increased to 40 patients to accommodate for data collection problems during the EP procedure. The following null-hypothesis H_0 and alternative hypothesis H_1 will be evaluated at a significance level of 0.05:

$$H_0: \Delta_{\text{MultiSpot SYN}} - \Delta_{\text{BiV}} \equiv 0\%$$

$$H_1: \Delta_{\text{MultiSpot SYN}} - \Delta_{\text{BiV}} \neq 0\%,$$

where Δ indicates percentage change from baseline for the corresponding configuration. Previous literature and results from the iSPOT study suggests that the average difference in percentage change between MultiSpot SYN and BiV pacing is 2.5% in a normal HF population (iSPOT-study, ^{9, 19}). For the standard deviation of the difference in % change between MultiSpot and BiV pacing we assume 7% based on previous literature and the iSPOT study.

Not much literature is available for the difference in % change between MultiSpot and BiV pacing for the study population targeted in this study. This study selects “difficult” CRT patients in order to adequately address the potential benefit of MultiSpot Pacing in this patient population. The term “difficult” represent those patients with an increased likelihood of non-response to conventional cardiac resynchronization therapy (e.g. ischemic patients or non-LBBB left ventricular dyssynchrony patients). Based on few small subgroup analyses (iSPOT study, ¹⁹), we expect that the difference in % change between MultiSpot SYN and BiV pacing will be slightly higher in the targeted study population, namely 3.5%. The sample size calculation is based on this difference of 3.5% and a standard deviation of 7%.

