3 electrodes on the LV wall will be paced sequentially. The RV-electrode will be paced simultaneously with last paced LV-electrode. The timing-sequence and the amount of spots will depend on the electrical delays measured during the experiments.

Configuration 5: LV lateral Apex → LV lateral Mid → LV lateral Base + RV

The different pacing settings include simultaneous and sequential RV and LV pacing and are in bipolar or unipolar mode. At each pacing site, the evaluation of the effect of CRT will be performed approximately 4 times (repetition) in order to increase signal to noise ratio. Each setting lasts about 20 beats (10-15 sec) interspersed with baseline (AAI; also 20 beats, 10-15 sec) pacing. The heart rate will be elevated by atrial pacing to a base rate about 10 beats above intrinsic or maximally tolerable rate, to ensure a constant heart rate. The RV-LV and the LV-LV (= VV-timing) intervals will be zero (MultiSpot-SYN) or will be sequential with VV-delay depending on the per patient measured electrical timing between the different electrode positions (MultiSpot-SEQ). For the latter, the VV-delay between Apical and Mid electrode position will be similar to the VV-delay between Mid and Basal electrode position. Optimal AV-delay will be calculated using CardioSync™ formulas ($PAV_{ECG} = \min(Ap-Pend + 30 \text{ ms}, Ap-RVs - 50 \text{ ms})$) derived from a correlation study between electrocardiographic measures such as the intrinsic AV interval and P-wave duration. The method aims at absence of truncation of the E/A waves. Up to five different AV-delays will be evaluated in this study (i.e. the optimal AV-delay and optimal AV-delay +/- 30 and +/- 60 ms). Hemodynamic measurements of positive LV dP/dt max, LV end diastolic pressure and arterial pressures will be measured during baseline and CRT. Additionally, at each pacing setting, the electrical delay from RV-pace to the different LV activations will be measured.

The signals from the LV pressure catheter, finger volume clamp system, internal electrograms, and surface ECG will be collected in real time and stored for later analysis as explained earlier. The CRT implant or EP procedure will be completed as per standard practice.

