The protocol procedures will result in an additional 30 to 45 minutes to the standard procedure time. Pacing will be achieved by using a Medtronic 2290 analyzer and temporary pacemaker (5388DDD or 5392) stimulators or equipment present in the operating room of the participating physicians.

All patients should be followed up according to standard of care after the end of the protocol procedures.

[figure not shown]

Figure 3: Start of protocol description.

Longitudinal MultiSPOT Pacing

[figure not shown]

Figure 4: Different ventricular lead positions. MultiSpot pacing at 3 electrodes at targeted LV locations synchronously or sequentially and RV. The mid and basal LV electrodes are placed in lateral or posterolateral vein. To reach the LV apex an alternative than the lateral vein can be used (to be anticipated the anterior vein). The delay between the different LV-electrodes will be determined during the experiment as it will be patient-dependent. AV-delay will be calculated using CardioSync™

Part A:

MultiSpot-SYN

- Place "Quadripolar lead" in CRT-target vein
- Place Guide-wire or second Multi-electrode lead in vein for apical electrode position
- Start RA-pacing (10-20 bpm above intrinsic rate or otherwise highest tolerable rate)

- Configuration 1: Pacing apical electrode. Run pacing protocol
- Configuration 2: Pacing mid electrode. Run pacing protocol
- Configuration 3: Pacing basal electrode. Run pacing protocol
- Configuration 4: Simultaneous pace all three electrodes. Run pacing protocol

Part B:

MultiSpot-SEQ

- Leave all leads at same position
- Determine timing between different electrodes (Apical, Mid and Basal)
- Calculate VV-delays
- Start RA-pacing (10-20 bpm above intrinsic rate or otherwise highest tolerable rate)

- Configuration 5: Sequential pace at all three electrodes. Run pacing protocol

Part C:

Pacing protocol

- Program optimal AV delay (and VV-delay in case of sequential pacing)
- Turn pacing 'on' via connection box during 10-15 sec
- Turn pacing 'off' via connection box during 10-15 sec
- Repeat ON/OFF 3 times (so 4 times in total)
- Program other AV delays (+/- 25 ms & +/- 50 ms) and repeat pacing protocol

[figure not shown]

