**Table 14: Measures**

Endpoint	Invasive/non-invasive	Tool
LV dP/dt max (mmHg/sec)	Invasive	LV catheter
Diastolic blood pressure (mmHg)	Invasive	Blood pressure transducer
Systolic blood pressure (mmHg)	Invasive	Blood pressure transducer
Diastolic blood pressure (mmHg)	Non-invasive	Finger volume clamp
Systolic blood pressure (mmHg)	Non-invasive	Finger volume clamp
QRS duration (msec)	Non-invasive	Surface ECGs
RV-LV timing (msec)	Invasive	Electrocardiogram
Q-LV interval (msec)	Invasive	Electrocardiogram and surface ECGs

LV dP/dt max and blood pressures are collected during the pacing protocol. The non-invasive blood pressures are collected optionally. RV-LV timing and Q-LV are collected during threshold testing and setup before the start of the pacing protocol.

The Q-LV interval is defined as the time from the onset of the QRS width of the surface ECG to the first large positive or negative peak of the LV electrogram (EGM) during a cardiac cycle. Percentage Q-LV (% Q-LV) will be calculated as the absolute Q-LV/QRS duration. Since there are three LV electrodes, the Q-LV interval can be determined for the apical, mid and basal LV electrode position.

The RV-LV timing gives the interval between intrinsic deflection of RV EGM and LV EGM. Since there are three LV electrodes, the RV-LV interval can be determined for the apical, mid and basal position. The following types of RV-LV timing (or LV-LV timing) might be collected:

- RV paced – LV sensed
- RV sensed – LV sensed
- LV paced – LV sensed
- LV paced – RV sensed

max	SBP			

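### All patients are listed for the same order of pacing configurations, with SEQ last, so a systematic mean trend in the response to pacing, if there is one, would bias the SEQ comparisons most

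*Protocol*

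**What the plan says.** **Order.** Protocol C.6: "No randomization and no blinding are used in this study". In the stepwise description in Protocol F.2.2, Part A runs the apical, mid and basal electrodes in turn and then SYN: "Configuration 4: Simultaneous pace all three electrodes. Run pacing protocol". Part B follows with the leads unmoved and ends with SEQ: "Configuration 5: Sequential pace at all three electrodes. Run pacing protocol". No sentence makes this order mandatory, and no readable sentence varies it.

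**Protection against drift.** Each pacing run of 10-15 s alternates with AAI pacing of equal length (Protocol F.2.2). The endpoint is % change from AAI, which SAP 7.9.1.2 justifies as a correction for baseline differences and drift. Protocol C.5.1 says the measurements were designed to limit within-subject temporal variation.

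**Model.** The per-patient regression in SAP 7.9.1.3, Step 1, contains configuration, AV delay, its square and interactions. It has no time or position term.

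**Why SEQ is last.** Protocol F.2.2 says of SEQ: "The timing-sequence and the amount of spots will depend on the electrical delays measured during the experiments". Part B measures the inter-electrode timing and calculates the VV-delays after Part A. Against this, Protocol B.2.1 has the hand-held pacers set before the experiment and then only switched on or off: "No additional intra-protocol settings will be changed". SAP 7.9.4.2 adds: "RV-LV timing and Q-LV are collected during threshold testing and setup before the start of the pacing protocol".

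**The concern.** Referencing each run to adjacent AAI pacing cancels a change in the AAI level. It does not cancel a change over the session in how much pacing adds to AAI. If every patient follows the listed order, a mean trend of that kind goes straight into the configuration contrasts, in proportion to the number of blocks between the two configurations.

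SEQ versus BiV basal has the widest gap among the comparisons in Protocol H.1. It is primary objective 2, and SAP 7.9.2.1 names it as the one of particular interest. An upward trend would favour SEQ and a downward trend would hide a benefit. Enlarging the sample does not remove a bias in the mean.

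**Working it through.** **Inputs.** N = 34, SD of the paired difference 7, assumed differences 3.5 (SYN-BiV) and 4 (SEQ-BiV), margin -3 with true difference +0.5 (Protocol C.7); two-sided 0.05, one-sided 0.025 for non-inferiority (Protocol H.1). The trend b, in percentage points of response per block, is an assumption. An unweighted paired t-test stands in for the SAP's weighted t-test, whose details are not readable.

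**1. The plan's own figures.** Standard error = 7/√34 = 1.200; noncentrality = difference/1.200; 33 df.
- SYN-basal: 3.5/1.200 = 2.92, power 80.8% (stated 80%; N = 33 gives 79.5%).
- SEQ-basal: 4/1.200 = 3.33, power 89.9% (stated 90%).
- Non-inferiority: (0.5 + 3)/1.200 = 2.92, power 80.8% (stated 80%).

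All three reproduce. The sample size is not in question.

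**2. Time between blocks.** 5 AV delays × 4 repetitions × (20 to 30 s on plus off) = 6.7 to 10 minutes per configuration. SYN starts 6.7-10 minutes after basal and SEQ 13-20 minutes after basal, before any set-up time.

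**3. What AAI referencing removes.** With a constant 10% response, a 20% drift in AAI over the session still gives 10.00% in all five blocks. A response trend of 0.5 points per block gives 10.0, 10.5, 11.0, 11.5 and 12.0.

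**4. Bias and error rates.** Positions are basal 3, SYN 4, SEQ 5. The bias is therefore b for SYN-basal, 2b for SEQ-basal and b for SEQ-SYN. The table gives the rejection probability with no true difference (non-inferiority: at a true -3).

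| b | SYN-basal (nominal 5%) | SEQ-basal (5%) | Non-inferiority (2.5%) |
|---|---|---|---|
| 0.25 | 5.5% | 6.9% | 3.9% |
| 0.5 | 6.9% | 12.8% | 6.0% |
| 1.0 | 12.8% | 36.6% | 12.5% |

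The nominal rate doubles at b = 0.81, 0.40 and 0.39 respectively. For SEQ-basal that is a bias of 0.81 points, about 6% of the 12.6 that Protocol C.7 assumes as the lower limit of the SYN response.

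With the trend reversed, power at b = 0.25 and 0.5 is:
- SYN-basal: 74.8% and 67.9% (from 80.8%)
- SEQ-basal: 80.8% and 67.9% (from 89.9%)
- Non-inferiority: 74.8% and 67.9% (from 80.8%)

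**5. Only the mean trend matters.** Simulated patient trends averaging zero (SD 0.5, 1 or 2 points per block) leave SEQ-basal error at 4.9-5.1%.

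**6. Can the analysis separate the two?** Position as a five-level factor cannot be separated from configuration under a common order. A linear time term can be fitted, because each configuration spans 20 runs. For 100 runs in the listed order (AV order partly assumed), the Step 1 terms plus time have full rank, 16 of 16. The slope has a standard error of about 1.2 residual SDs per block in one patient, or 1.2/√34 = 0.2 averaged over 34.

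At zero AV offset, the prediction variance for one configuration is 17/140 of the residual variance. The SEQ-basal contrast without the time term therefore has SE √(2 × 17/140) = 0.49 residual SDs. With the term it is √(0.49² + (2 × 1.2)²) = 2.45, about five times larger.

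**The case against.** The strongest defence is that the plan already handles the most familiar time effect. Baseline is re-measured every 10-15 s and the endpoint is relative to it. What remains needs a systematic mean change in the incremental response over some 13-20 minutes. Nothing in the documents shows one, and every b above is assumed. This stands: the concern is conditional, and for SYN-basal it is small at small trends.

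The study is also declared exploratory (Protocol H.1; SAP 7.5). That is the stated reason for not adjusting for multiplicity. It does not make an order-dependent contrast easier to interpret.

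Four stronger readings are tempting and are not supported:
- *The SEQ result is biased.* The documents give neither the existence nor the direction of a trend.
- *The trend acts the same way in every patient.* A common order fixes the sign of the position gap, not of each patient's trend. Step 5 shows that trends averaging zero do no harm.
- *No analysis could address it.* A linear time term can be fitted. It is too imprecise to be more than a sensitivity analysis.
- *SAP 7.9.4.2 contradicts Part B.* In Protocol F.2.2 the pacing protocol can mean Part C, run afresh for each configuration, and then the two texts agree. SAP 5.3.1 uses the term more broadly, so this is an ambiguity. SAP 7.9.4.2 also concerns the correlation measures, not VV-delay programming. The clear tension is Protocol B.2.1 against F.2.2.

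Figures and part of the SAP analysis section are not readable, so a time term there cannot be excluded. It could not separate position as a factor from configuration.

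**Conclusion.** The point holds as a conditional design weakness and a cheap improvement, not a fatal flaw. One order is listed, none is rotated, and AAI referencing does not cover a mean trend in the response itself. At an assumed 0.5 points per block, error is 12.8% for SEQ-basal, 6.9% for SYN-basal and 6.0% for non-inferiority, or SEQ-basal power falls to 67.9% if the trend runs the other way. These figures rest on a linear mean trend, the listed order in all patients, 34 evaluable patients, SD 7 and an unweighted test. The SEQ comparisons are the main concern.

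**What to change.** 1. **Reconcile the texts.** Make Protocol B.2.1 and F.2.2 agree on when electrode timings and VV-delays are determined and programmed, and clarify what SAP 7.9.4.2 means by the start of the pacing protocol. The answer decides between steps 2 and 3.

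2. **If the timings can be available before the first block,** run the five configurations in a pre-generated balanced order, for example a 10-sequence Williams list used four times (4 × 10 = 40). Record position and include a linear position term in the between-configuration comparisons. With 34 of 40 evaluable (2,000 random draws), power is 80.5% against 80.8% for objective 1 and 89.7% against 89.9% for objective 2. A four-df position term gives 79.7% and 89.0% and suits a sensitivity analysis. The list should be kept balanced: unrestricted random orders average 79.5% for objective 1 with the linear term.

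3. **If SEQ must stay last,** keep its position, record run times, add a linear-time sensitivity analysis to the SAP, and state position confounding as a limitation of the SEQ comparisons. Swapping basal and SYN in half of the patients is not recommended as a default. Both would then average position 3.5, which removes the SYN-basal bias and cuts SEQ-basal from 2b to 1.5b, but raises SEQ-SYN from b to 1.5b. At b = 0.5, SEQ-basal error falls from 12.8% to 9.3% while non-inferiority error rises from 6.0% to 8.8%.

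**Cost.** Step 2 needs a protocol amendment, a SAP line, a sequence list held across about 10 sites and some reprogramming around the SEQ block. The last is not free: full pacing runs already take 5 × (6.7 to 10) = 33 to 50 minutes, against the 30 to 45 extra minutes that Protocol F.2.2 allows. Step 3 needs SAP text and recorded run times. Neither needs more patients.

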Exclusion criteria	
 • Subject has permanent atrial fibrillation/flutter or tachycardia • Subject has pure right bundle branch block (= no additional left ventricular conduction delays) • Subject has left bundle branch block and QRS-duration of > 150 ms and no sign of myocardial scar indicated by late gadolinium enhancement MRI • Subject experienced recent myocardial infarction, within 40 days prior to enrollment • Subject underwent valve surgery, within 90 days prior to enrollment • Subject is post heart transplantation, or is actively listed on the transplantation list • Subject is implanted with a left ventricular assist device • Subject has severe renal disease (up to physicians discretion) • Subject is on continuous or uninterrupted infusion (inotropic) therapy for heart failure (≥ 2 stable infusions per week)

	
 • Subject has severe aortic stenosis (with a valve area of <math><1.0\text{ cm}^2</math> or significant valve disease expected to be operated within study period) • Subject has complex and uncorrected congenital heart disease • Subject has a mechanical heart valve • Pregnant or breastfeeding women, or women of child bearing potential and who are not on a reliable form of birth control • Subject is enrolled in another study that could confound the results of this study, without documented pre-approval from Medtronic study manager

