There will be no minimum limit that each investigator must enroll. To ensure a widespread distribution of data between centers, the maximum number of enrolled subjects per center is 15 subjects.

D SUBJECT SELECTION

D.1 Inclusion criteria

- Subject is indicated or recommended for CRT-P or CRT-D device according to the current ESC/AHA guidelines
- Subject is in sinus rhythm
- Subject receives optimal heart failure oral medical therapy
- Subject is willing to sign the informed consent form
- Subject is 18 years or older

D.2 Exclusion criteria

- Subject has permanent atrial fibrillation/flutter or tachycardia
- Subject has pure right bundle branch block (= no additional left ventricular conduction delays)
- Subject has left bundle branch block **and** QRS-duration of > 150 ms **and** no sign of myocardial scar indicated by late gadolinium enhancement MRI
- Subject experienced recent myocardial infarction, within 40 days prior to enrollment
- Subject underwent valve surgery, within 90 days prior to enrollment
- Subject is post heart transplantation, or is actively listed on the transplantation list
- Subject is implanted with a left ventricular assist device
- Subject has severe renal disease (up to physicians discretion)
- Subject is on continuous or uninterrupted infusion (inotropic) therapy for heart failure (≥ 2 stable infusions per week)
- Subject has severe aortic stenosis (with a valve area of <1.0 cm² or significant valve disease expected to be operated within study period)
- Subject has complex and uncorrected congenital heart disease
- Subject has a mechanical heart valve
- Pregnant or breastfeeding women, or women of child bearing potential and who are not on a reliable form of birth control
- Subject is enrolled in another study that could confound the results of this study, without documented pre-approval from Medtronic study manager

E STUDY PREPARATION PROCEDURES

E.1 Investigator/Investigation site selection

The role of the principal investigator is to implement and manage the day-to-day conduct of the clinical study as well as ensure data integrity and the rights, safety and well-being of the subjects involved in the clinical study.

An investigator/investigation site may be included in the investigation, if the investigator/investigation site complies with the following requirements:

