- Multi-lead ECG (within last 3 months, otherwise a new ECG should be performed)
- Echocardiographic evaluation (if available within last 3 months, otherwise not collected)
- NYHA classification
- Medical history (cardiovascular or related)
- Cardiovascular medications

- Pregnancy test for women with child-bearing potential
- MRI as explained in paragraph below

F.2.1.1 Magnetic Resonance Imaging (MRI)

Patients will undergo a baseline MRI before scheduled CRT-related surgery (i.e. dedicated research study or EP procedure or actual CRT implant) to identify the location and transmural of any myocardial scar using late gadolinium enhancement-magnetic resonance imaging according to standard hospital practice. During the MRI a thorax scan is required to be able to reconstruct the thorax and lungs, i.e. a transverse scan with neck and liver visible. An appropriate marker should be placed on the xyphoid and 10 cm above the xyphoid during this scan. In addition, left ventricular end systolic volume (LVESV), left ventricular end diastolic volume (LVEDV) and left ventricular ejection fraction (LVEF) will be determined. MRI can be performed as standard of care or solely for the study. If the patient has a LBBB conduction pattern and QRS-width above 150ms, the MRI images should be analyzed before the EP study to detect the presence of scar. If no scar is present on late gadolinium enhancement MRI, the LBBB patient with QRS > 150ms should not be included in the study (if MRI done as standard of care) or should be exited from the study (if MRI done solely for the study).

F.2.2 Electrophysiological (EP) study visit

The EP study visit can be a standalone visit or can occur on the same day as the baseline visit. The EP study visit should take place within 3 months after the MRI has been obtained. Patients will undergo standard implant of a biventricular pacing system (CRT-P or CRT-D) or will undergo the EP study (data for this research study will be collected) before possible CRT-implant or will participate in this dedicated research study as a standalone visit (without any concomitant procedure).

If available in the center, a finger volume clamp system (e.g. model Nexfin, BMEYE B.V.) will be connected to one of the subject's fingers to measure the blood pressure non-invasively. In addition, a multi-lead surface ECG is collected during the whole procedure.

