¹ In case the MRI is done solely for the study: If the patient has ischemic etiology and a LBBB conduction pattern and QRS-width above 150ms, the MRI images should be analyzed immediately to detect scar. If scar is not present on late gadolinium enhanced MRI, the patient should be exited from the study prior to EP visit

F.4 Role of the sponsor’s representatives

Sponsor’s representatives (e.g. Field Clinical Engineer, Field CRS, Technical Consultant) may provide support as required for the clinical study, including technical support during implant/procedure including completion of a technical support sheet and/or technical support. Documentation of study training and qualification of sponsor representatives will be maintained by Medtronic. The sponsor’s representatives providing technical support may be listed on the sponsor technical support list.

F.5 Source documents

Source documents may be the PIC, hospital/clinic files, Electronic Media (MRI images, Echo images), programmer or ECG printouts, worksheets, MRI images and eCRFs.

The investigator will clearly mark the clinical records to indicate that the subject is enrolled in this clinical study.

Data that could be recorded directly on the eCRF and considered as source data are listed in section G.1.2.

F.6 Adverse events and Device Deficiencies

F.6.1 Definition/classification

Timely, accurate, and complete reporting and analysis of safety information for clinical studies are crucial for the protection of subjects, investigators, and the sponsor. Reporting and analysis of safety data are mandated by regulatory authorities worldwide. All events and deaths for the SYNSEQ study will be collected, classified, reviewed and reported from enrollment up till study exit. Documented pre-existing conditions are not considered AEs unless the nature or severity of the condition has worsened.

For the purposes of the clinical report, Medtronic will classify each Adverse Event according to ISO 14155:2011.

Where the definition indicates “device”, it refers to any device used in the study. This might be the device under investigation, or any market released component of the system.

Adverse Event (AE): (ISO14155:2011 3.2)

Any untoward medical occurrence, unintended disease or injury, or untoward clinical signs (including abnormal laboratory findings) in subjects, users or other persons, whether or not related to the investigational medical device

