With regard to individual subjects, no dedicated closure visit will occur in association with overall study closure, and no medical care as defined by the study will be provided to the subject following overall study closure.

H DATA ANALYSIS AND REPORTING

A detailed description of the statistical methods will be contained in the Statistical Analysis Plan. Any changes to the data analysis methods will be described and justified in the Final Report or publication.

H.1 Analysis of clinical data

Descriptive statistics will be used to summarize the patient demographic and clinical characteristics at baseline. Data for qualitative variables will be presented as incidence rates (total number of patients, number of events, and percent). Data for continuous variables will be summarized using measures of central tendency and dispersion.

P-values for hypothesis testing will be evaluated based on a two-sided significance level of 0.05 except for the secondary objective 1 which is evaluated using a one-sided significance

level of 0.025. No adjustments will be made for multiple testing because of the exploratory nature of this study. No imputation of missing data is planned. No interim reports are planned for this study.

Any change to the data analysis methods described in the Clinical Investigational Plan will require an amendment only if it changes an objective of the Clinical Investigational Plan. Any other change to the data analysis methods described in the Clinical Investigational Plan, and the justification for making the change, will be described in the clinical study report. Additional exploratory analyses of the data will be conducted as deemed appropriate.

All patients who signed the informed consent document will be defined as the enrolled population. The Analysis Population is defined as patients who are enrolled, have no inclusion or exclusion criteria violation regarding the most important criteria, i.e., inclusion criteria 1 and 2 and exclusion criterion 3, and for whom the EP procedure could be completed successfully. Patients, who are not part of the Analysis Population, will not be included in the primary analysis of the primary objectives, but will be reported in the patient disposition table. A secondary analysis might be performed including patients who have eligibility violations. Safety will be reported on the All Enrolled Population and the primary objectives will be reported on the Analysis Population.

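### Table 2 footnote 1 ties the pre-EP scar check and exit to ischemic etiology, a condition absent from exclusion criterion 3, the synopsis and F.2.1.1

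*Protocol*

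**What the plan says.** Exclusion criterion 3 reads, in the protocol synopsis: "Subject has left bundle branch block and QRS-duration of > 150 ms and no sign of myocardial scar indicated by late gadolinium enhancement MRI". D.2 and SAP 5.2.2 state the same three conditions. None mentions etiology.

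F.2.1.1 turns the criterion into a procedure. For a patient with LBBB and "QRS-width above 150ms, the MRI images should be analyzed before the EP study to detect the presence of scar". It continues: "If no scar is present on late gadolinium enhancement MRI, the LBBB patient with QRS > 150ms should not be included in the study" when the MRI was standard of care; when the MRI was done only for the study, the patient is exited. The baseline MRI item in the synopsis gives the same rule without an etiology condition.

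Footnote 1 to Table 2 is attached to the baseline cell of the Exit row. It opens "In case the MRI is done solely for the study", sets the condition "If the patient has ischemic etiology and a LBBB conduction pattern and QRS-width above 150ms", asks for an immediate reading, and ends: "If scar is not present on late gadolinium enhanced MRI, the patient should be exited from the study prior to EP visit".

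Protocol H.1 and SAP 7.1.3 define the Analysis Population by the absence of violations of "inclusion criteria 1 and 2 and exclusion criterion 3".

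**The concern.** One rule is stated with two different scopes. The footnote adds a condition that removes some patients from its reach, and it does so on the Exit row of the data-collection schedule, which site staff are likely to use as a checklist.

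The exit step matters for a study-only MRI. Written consent must come before any study activity (E.2.2), and signing it is enrollment (F.1). When the MRI is done only for the study, criterion 3 can therefore be settled only after the patient is enrolled, and exit is what keeps a no-scar patient out of the EP study. The baseline visit and the EP study may also fall on the same day (F.2.1, F.2.2), which leaves little time to notice an omission.

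What is at stake is avoidable exposure. The EP study involves femoral arterial access, a pressure catheter in the left ventricle and heparin (F.2.2), together with contrast, 30 to 45 minutes of procedure time and about 10 minutes of fluoroscopy (J.2). J.1 states that participants get no immediate direct benefit. A patient who meets criterion 3 would bear this without contributing to the primary analysis.

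**Working it through.** No figure in the plan depends on this point, so the check is a comparison of texts. Take a patient with LBBB, QRS above 150 ms and no scar, and vary the two features on which the statements could differ: etiology and the reason for the MRI.

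| Etiology | Reason for MRI | Exclusion criterion 3 | F.2.1.1 | Table 2 footnote 1 |
|---|---|---|---|---|
| Ischemic | Study only | Excluded | Read before EP study; exit | Read immediately; exit before EP visit |
| Non-ischemic | Study only | Excluded | Read before EP study; exit | No instruction |
| Ischemic | Standard of care | Excluded | Read before EP study; not included | Does not apply |
| Non-ischemic | Standard of care | Excluded | Read before EP study; not included | Does not apply |

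1. Criterion 3 and F.2.1.1 agree in all four rows, and the synopsis MRI rule also excludes the patient in each.
2. The footnote applies to the first two rows only, because it is limited to study-only MRIs.
3. Within those two rows it agrees with the other statements for the ischemic patient and is silent for the non-ischemic one. The mismatch is the second row.
4. SAP Table 4 offers a cross-check on the intended population. Its total row counts patients with no LBBB, or QRS of at most 150 ms, or LBBB with QRS above 150 ms and scar. Etiology does not appear there either, so the footnote is the only statement that carries the condition.
5. Consequence for the analysis: a second-row patient who undergoes the EP study violates criterion 3 and is removed from the Analysis Population under both the protocol and the SAP definition. The data could appear only in the optional secondary analysis.

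**The case against.** The strongest answer is that the rest of the protocol closes the gap. F.2.1.1 is the section that governs the MRI, and it requires the reading and the exit regardless of etiology. F.2.1 has every eligibility criterion verified at baseline, Table 2 itself carries an eligibility row at that visit, and C.4 and C.8 require that no exclusion criterion be met. The footnote does not say that other patients are exempt; it gives an instruction for one subgroup. A site that skipped the check would be deviating from the protocol.

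This stands, and it limits the finding. A reader might infer that the protocol permits non-ischemic no-scar patients to enter the EP study. It does not. They could enter only if a site followed the footnote in place of those sections. The objection does not remove the contradiction: the footnote is an operative exit instruction, and it is narrower than the criterion it implements.

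Two further inferences are not supported:

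- **Loss of power.** A no-scar patient gives no primary data whether exited before the EP study or removed afterwards, so correcting the footnote recovers no evaluable patient. The plan also has a reserve. With its own inputs (difference 3.5, SD 7, two-sided 0.05, paired t-test), power is 80.8% at 34 patients and 86.9% at the planned 40. Six of the 40 could be lost for any reason (40 − 6 = 34) with power still above 80%.
- **Dilution of the target population.** Patients identified as violating criterion 3 are removed from the primary analysis. The finding in B.1 of no added effect from multisite pacing concerns responders with strictly defined LBBB, not all LBBB patients.

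**Conclusion.** Wrong as written: an internal contradiction of minor severity. Footnote 1 covers one of the two study-only groups that criterion 3 and F.2.1.1 cover, and omits non-ischemic patients with LBBB, QRS above 150 ms and no scar.

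Its size in patients is unknown. The documents do not give the share of study-only MRIs, the share of non-ischemic patients, or how often scar is absent in either etiology group. It would therefore also go beyond the documents to say that the omitted patients are those most likely to lack scar. Each patient missed would mean one invasive procedure with no contribution to the primary analysis.

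The conclusion rests on two assumptions: that a site might work from Table 2 without returning to F.2.1.1, and that the MRI is read for scar at some point, so that the violation is recognised and the patient removed from the Analysis Population. The second is reasonable, since F.2.1.1 gives locating scar as the purpose of the baseline MRI.

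**What to change.** Reconcile Table 2 footnote 1 with exclusion criterion 3, the synopsis MRI rule and F.2.1.1, so that all four describe the same patients. If criterion 3 stands as written in D.2 and SAP 5.2.2, taking the words on ischemic etiology out of the footnote is enough to make it match. A cross-reference from the footnote to F.2.1.1 would keep the two aligned.

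The cost is one phrase in a protocol footnote and notice to the sites. Every patient already has a baseline MRI, so no imaging is added. The eligible population, the Analysis Population and the statistical methods stay as they are, and the SAP needs no change.
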